we have conducted a prospective study of 40 patients with myocardial infarction in whom 18F-fluoride localised to the culprit plaque (Figure 1) in over 90% of patients [Joshi *et al*, 2013]. This finding was confirmed in 12 patients with a recent stroke undergoing carotid endarterectomy where 18F-fluoride uptake was observed at the site of plaque rupture in 100% of patients and this uptake correlated with increased calcification activity and areas of necrosis on histology. Finally we studied 40 patients with stable coronary artery disease. Increased uptake was observed in 45% of these patients and this again localized to individual coronary plaques (Figure 2). Interestingly these lesions were associated with multiple high-risk markers on radiofrequency and gray-scale intravascular ultrasound (necrotic core, positive remodeling and microcalcification). Importantly, plasma high-sensitivity troponin concentrations were much higher in patients with 18F-fluoride positive plaques compared with patients without evidence of uptake (7.89 ± 9.34 versus 3.10 ± 1.89 ng/L, $P=0.047$; Figure 3). The latter observation is of particular interest as it supports the hypothesis that 18F-fluoride is detecting subclinical plaque rupture in those with stable disease, similar to its mechanism of activity following myocardial infarction. Moreover plasma troponin concentrations measured by a high-sensitivity assay also predict an adverse outcome amongst patients with stable coronary artery disease [Omland *et al*, 2013] and provide a useful surrogate biomarker of therapeutic efficacy.

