2.1.2 Secondary Objectives

- a) To assess whether ticagrelor will reduce plasma high-sensitivity troponin concentrations in patients without increased coronary 18F-fluoride uptake.
- b) To assess whether ticagrelor will reduce plasma high-sensitivity troponin concentrations over a 1-year time frame.
- c) To assess whether ticagrelor will reduce coronary plaque volume or calcium score at the site of 18F-fluoride uptake.
- d) To confirm the reproducibility of 18F-fluoride PET positivity
- e) To assess the natural history of 18F-fluoride PET positive coronary plaque

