2.2.2 Secondary Endpoints

- a) Plasma hsTnI concentrations at 30 days in patients without coronary 18F-fluoride uptake.
- b) High sensitivity cardiac troponin I (hsTnI) concentration at 30 days in total study population.
- c) Plasma hsTnI concentrations over 1 year
- d) Calcium score at 1 year
- e) Plaque volume at 1 year
- f) Reproducibility of 18F-fluoride uptake detected on PET imaging at 1 week
- g) Natural history of 18F-fluoride uptake over 1 year

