The positron emission tomography scans will be reconstructed in multiple phases of the cardiac cycle, with the diastolic phase (50-75%) used for analysis. The computed tomography coronary angiography scans will be reconstructed at 0.75 x 0.7 mm and 0.6 x 0.3 mm for retrospective and prospective acquisitions respectively at 60%, 65% and 70% of the cardiac cycle. Additional reconstructions will be undertaken as necessary. Positron emission tomography scans will correct for cardiac motion correction using electrocardiogram-gated images.

18F-F PET Natural History Sub-study

Using the same scan process as outlined above a sub-group of patients will be selected for 1 additional PET scan. In total this will involve 80 patients out of the total cohort. The first 20 participants to be scanned will be to assess the reproducibility of 18F-fluoride uptake and will undergo a second PET scan at the randomisation visit (1 week after the baseline scan). This group will comprise 10 patients from both of the PET positive and PET negative samples. Following this we will investigate the natural history of 18F-fluoride uptake by performing repeat PET scans on 60 patients in total from the initial PET positive sample with 20 patients scanned at the 3 month, 6 month and 12 month follow up visits. No individual patient will undergo more than 2 PET scans during the course of the study. In order to allow accurate co-registration of images, repeat CT coronary angiograms will be performed at the time of the repeat PET scans. The additional PET scan for those in the sub-study will be performed at the 1 week, 3 month, 6 month or 12 month visit but the additional CTCA scan will only be performed at 1 week, 3 month or 6 month visits as the CTCA scan at 12 months will be performed on all participants irrespective of whether they are taking part in the sub-study

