#### *7.5.6 Reproducibility of 18F-fluoride uptake detected on PET imaging at 1 week.*

Within the group entered into this sub-study, descriptive statistics will be presented. This will include the proportion of PET positive patients at 1 week, among those who were PET positive at baseline; and the proportion of PET negative patients at 1 week, among those who were PET negative at baseline. Crude overall agreement will be presented, along with a kappa statistic (with the understanding that the margins were fixed in the design of this study).

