#### *7.5.7 Natural history of 18F-fluoride uptake over 1 year.*

Tables will be produced to summarise the groups of patients measured at baseline and 3 months, baseline and 6 months, and baseline and 1 year. Descriptive statistics will show the proportion of PET positive/negative patients at the later time point, among those who were PET positive at baseline; and the proportion of PET positive/negative patients at the later time point among those who were PET negative at baseline.

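### SAP 7.5.7 reduces the natural history of 18F-fluoride uptake to PET positive or negative in patients who all start positive, so a rise, or a fall that stays above the cut, counts as no change

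*SAP*

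**What the plan says.** Protocol 2.2.2 lists two PET secondary endpoints: (f) "Reproducibility of 18F-fluoride uptake detected on PET imaging at 1 week" and (g) "Natural history of 18F-fluoride uptake over 1 year". The matching objectives in Protocol 2.1.2 are worded a little differently: (d) "To confirm the reproducibility of 18F-fluoride PET positivity" and (e) "To assess the natural history of 18F-fluoride PET positive coronary plaque".

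Protocol 7.2.4 fixes the samples. The reproducibility group is 20 patients (10 PET positive, 10 PET negative), rescanned at about 1 week. For the rest: "Following this we will investigate the natural history of 18F-fluoride uptake by performing repeat PET scans on 60 patients in total". These 60 come from the PET positive sample, 20 at each of 3, 6 and 12 months. CT angiography is repeated with the second PET scan so that the images can be co-registered.

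SAP 7.5.7 then plans, for each time point: "Descriptive statistics will show the proportion of PET positive/negative patients at the later time point, among those who were PET positive at baseline", and the same for baseline negatives. SAP 7.5.6 plans the proportions confirmed positive and confirmed negative at 1 week, and: "Crude overall agreement will be presented, along with a kappa statistic". Neither section names an uptake value, a paired change, a confidence interval or a measurement error.

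**The concern.** In 7.5.7 every patient starts on the same side of the cut. The table can record only one event, loss of positivity. A plaque whose uptake doubles, or whose uptake halves but stays above the cut, is entered as still positive. Endpoint (g) asks how uptake behaves, and still positive answers that only in part.

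There is a second difficulty. Patients chosen because they were above a cut will on average read lower the next time, even if nothing has changed. Some will cross the cut through measurement error alone. A bare proportion still positive mixes that with real change, and 7.5.7 sets no reference against which to separate them.

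At stake is the value of a sub-study in which 80 patients accept a second PET/CT. Protocol 12.6.2 puts the research radiation dose at 46 mSv for most of them (38 mSv if rescanned at 12 months) against 30 mSv otherwise. The same SAP treats calcium mass and volume as continuous, with baseline, 1-year and change summaries (7.5.4, 7.5.5), and gives no reason for handling uptake differently.

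**Working it through.** **The plan's own figure.** There is none to reproduce. The PET sub-study has sizes (20 + 3 × 20 = 80) but no stated power or precision. The only input the documents supply is the 60% prevalence of coronary uptake (Protocol 9.1). Everything else below is an assumption.

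**Step 1. What the table can show.** The 60 natural-history patients are all positive, and Protocol 7.2.4 allows nobody more than two PET scans. So the baseline-negative row of 7.5.7 is empty by design, and each 20-patient table reduces to one proportion. If 16 of 20 remained positive, the exact 95% CI would be 56% to 94%.

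**Step 2. Information kept by the yes/no reading.** Assume standardised (log) uptake, baseline X and repeat Y bivariate normal with correlation ρ, and a mean shift d in Y.

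- Cut: c = Φ⁻¹(0.40) = −0.253. Also λ = φ(c)/0.60 = 0.386/0.60 = 0.644.
- Variance of X among positives: v = 1 + cλ − λ² = 1 − 0.163 − 0.415 = 0.422.
- Variance of the change Y − X among positives: V = (1 − ρ)²v + 1 − ρ².
- Probability of remaining positive: p(d) = (1/0.60) ∫ from c to ∞ of φ(x) Φ((ρx + d − c)/√(1 − ρ²)) dx.
- Information about d per patient: p′(d)²/[p(1 − p)] for yes/no, 1/V for the change score. Fraction kept = p′²V/[p(1 − p)].

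Worked case at ρ = 0.80, d = 0: V = 0.04 × 0.422 + 0.36 = 0.377; p = 0.835; p′ = 0.344; fraction = 0.344² × 0.377/(0.835 × 0.165) = 0.32.

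| Correlation ρ | Still positive with no true shift | Fraction of information kept |
|---|---|---|
| 0.3 | 68% | 0.70 |
| 0.5 | 73% | 0.56 |
| 0.7 | 80% | 0.41 |
| 0.8 | 83% | 0.32 |
| 0.9 | 88% | 0.22 |
| 0.95 | 92% | 0.15 |

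With 45% above the cut (the proportion in the earlier stable-disease cohort, Protocol 1.1.3) the fractions run from 0.72 to 0.19.

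**Step 3. Regression to the mean.** The middle column shows 8% to 32% losing positivity with no true shift. On the continuous scale the same selection gives an expected fall of (1 − ρ)λ; at ρ = 0.80 this is 0.20 × 0.644 = 0.13 SD. Either reading needs the 1-week repeat in baseline positives as a reference.

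**Step 4. Precision of the addition.** For 20 patients, the 95% half-width of a mean change is 2.093/√20 = 0.47 SD of change. For the 10 reference patients it is 2.262/√10 = 0.72. For the difference between them, assuming equal SDs, it is 2.048 × √(1/20 + 1/10) = 0.79. So the reference is useful but imprecise.

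**Step 5. Reproducibility.** With 9 of 10 concordant in each stratum, observed agreement is 0.90, chance agreement 0.50 and kappa 0.80. SE = √(0.9 × 0.1/20)/0.5 = 0.134, so the 95% CI runs from 0.54 to the ceiling of 1. With 10 of 10 confirmed, the exact lower limit is 0.025^(1/10) = 69%. These describe positivity. They give no error in uptake units, which is what a later change in uptake has to be judged against.

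**The case against.** Much can be said for the plan.

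- Objective (d) is about positivity. The proportions and kappa in 7.5.6 answer it directly, and the section introduces its list as items that will be included, so the list is not closed. This stands. The gap there is only that endpoint (f) speaks of uptake.
- Coronary uptake is used in this trial as present or absent: population, minimisation, primary endpoint, interaction term. The statement that "this uptake correlated with increased calcification activity and areas of necrosis on histology" comes from 12 carotid endarterectomy patients in previous work, so it is thin evidence that coronary uptake here is to be read as a graded quantity. This stands too, but it does not make a yes/no table a full description of uptake over a year.
- Protocol 3.1 calls the component exploratory. Protocol 2.2.2 and SAP 7.5 nevertheless carry it as secondary, and the exploratory objectives in Protocol 2.1.4, which SAP 7.8 sets aside, do not include repeat uptake.
- No supplied text says that a numerical uptake value is recorded, and SAP 7.5.5 shows that an intended imaging measure can prove unavailable. The cost is therefore probably small but not certain.

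A reader might infer that there is a large and general loss of power. The documents do not support that. Both analyses are descriptive and no test is planned. If one invents a test of 20 natural-history against 10 reproducibility positives, the size of the gap depends on the assumptions and on the binary test used. With a mid-p exact test, reliability 0.80 to 0.95 and SD of true change 0.3 to 0.6, a 0.5 SD fall gives about 22–39% (binary) against about 42–93% (Welch t on the change). At reliability 0.80, SD of change 0.6 and a 0.3 SD fall, the gap is only about 4 points. The direction is consistent, but no minimum gain can be promised.

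**Conclusion.** The point holds for SAP 7.5.7. Its only named summaries are positive/negative, all 60 patients start positive, and a rise in uptake, or a fall that stays above the cut, cannot appear as a change. This follows from the text alone and needs no assumption.

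The size does need assumptions. Under the normal model with 60% above the cut, the yes/no reading keeps about 70% down to 15% of the information in a change score as the correlation goes from 0.3 to 0.95. More than half is lost at correlations of about 0.7 and above, but not at 0.5 or below.

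A reader might go further and infer that both PET endpoints lose most of their information. That cannot be derived: the correlation is not given, and for reproducibility the binary analysis matches objective (d). For 7.5.6 the point is only that a measure of error in uptake units is missing for endpoint (f). The primary analysis and the treatment comparisons are unaffected.

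**What to change.** **SAP 7.5.7.** Name one continuous uptake measure at the co-registered baseline site, on the log scale if skewed, with its definition. Report the mean paired change with 95% CI at 3, 6 and 12 months. Show beside it the mean 1-week change in the 10 baseline-positive reproducibility patients, so that true change can be told from regression to the mean, and say that this reference is imprecise. Keep the positive/negative tables.

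**SAP 7.5.6.** Keep the proportions, crude agreement and kappa for objective (d). For endpoint (f) add the mean test-retest difference with limits of agreement, or an intraclass correlation with 95% CI. For illustration, an observed value of 0.90 in 20 patients would have a 95% CI of 0.77 to 0.96. That is not comparable with the kappa interval, since the two measure different things.

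**Cost.** SAP wording, plus modest reading time if the value is not already recorded. No extra scans, visits or patients. The measure must be fixed before the repeat values are analysed. If it turns out that no usable value can be obtained, the SAP should say so and state that the tables describe positivity only.

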### **7.6 Safety analyses**

These analyses will use the safety population. Adverse Events (AEs) will be summarised by treatment received and by seriousness, causality, expectedness, and severity of event. If available, events will be reported by MedDRA preferred terms and grouped by System Organ Class. If a patient has multiple reports of the same event, only the event reported at the highest grade will be included. Each patient will be counted only once in a summary of events by System Organ Class. No formal statistical analysis will be

performed. A listing will be produced detailing each event, and what happened to the patient subsequently.

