10.4.2 Assessment of Causality

The Investigator will make an assessment of whether the AE/SAE is likely to be related to the IMP according to the definitions below.

- Unrelated: where an event is not considered to be related to the IMP.
- Possibly Related: The nature of the event, the underlying medical condition, concomitant medication or temporal relationship make it possible that the AE has a causal relationship to the study drug. The assessment of causality will be made against the reference safety information found in the Summary of Product Characteristics.

Where non Investigational Medicinal Products (NIMPs) e.g. rescue/escape drugs are given: if the AE is considered to be related to an interaction between the IMP and the NIMP, or where the AE might be linked to either the IMP or the NIMP but cannot be clearly attributed to either one of these, the event will be considered as an AR. Alternative causes such as natural history of the underlying disease, other risk factors and the temporal relationship of the event to the treatment should be considered and investigated. The blind should not be broken for the purpose of making this assessment.

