10.4.4 Assessment of Severity

The Investigator will make an assessment of severity for each AE/SAE and record this on the CRF or SAE form according to one of the following categories:

Mild: an event that is easily tolerated by the participant, causing minimal discomfort and not interfering with every day activities.

Moderate: an event that is sufficiently discomforting to interfere with normal everyday activities.

Severe: an event that prevents normal everyday activities.

Note: the term 'severe', used to describe the intensity, should not be confused with 'serious' which is a regulatory definition based on participant/event outcome or action criteria. For example, a headache may be severe but not serious, while a minor stroke is serious but may not be severe.

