#### **7.6.1 Bleeding**

These analyses will use the safety population. To determine whether the addition of ticagrelor to standard optimal medical therapy is safe and well tolerated in patients with stable coronary heart disease on optimal medical therapy.

All bleeding events will be summarised by treatment received and categorised according to the 2009 PLATO criteria [Wallentin et al, 2009]. No formal statistical analysis will be performed. Time to each bleeding event from study entry and description of the bleeding event will be provided.

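### SAP 7.6 keeps only the highest-grade report of a repeated adverse event in every summary, so serious or related reports can drop out of the seriousness and causality tables

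*SAP*

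**What the plan says.** SAP 7.6 (Safety analyses) states that adverse events will be "summarised by treatment received and by seriousness, causality, expectedness, and severity of event". For repeats it adds: "If a patient has multiple reports of the same event, only the event reported at the highest grade will be included". The next sentence reads: "Each patient will be counted only once in a summary of events by System Organ Class". The section does not say which tables the highest-grade rule covers, and it gives no other rule for choosing among repeated reports. It defines neither 'grade' nor 'same event', and MedDRA terms are to be used only if available.

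Protocol 10.4.4 supplies the only intensity scale for general adverse events: "The Investigator will make an assessment of severity for each AE/SAE and record this on the CRF or SAE form according to one of the" three listed levels, mild, moderate and severe. The same section warns against confusing severe with serious and illustrates the difference: "a headache may be severe but not serious, while a minor stroke is serious but may not be severe". Causality is a separate judgement under protocol 10.4.2: "The Investigator will make an assessment of whether the AE/SAE is likely to be related to the IMP according to the definitions below".

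Two other outputs bear on the point. SAP 7.6 promises: "A listing will be produced detailing each event, and what happened to the patient subsequently". SAP 7.6.1 says: "All bleeding events will be summarised by treatment received and categorised according to the 2009 PLATO criteria".

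**The concern.** The rule chooses a report by its intensity, and that report's other attributes then feed tables that are not about intensity. This is sound for a severity table, where the worst grade is the quantity wanted. It is not sound for seriousness, which depends on outcome or action (protocol 10.1), or for causality, which is an attribution judgement.

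Take a patient with mild dyspnoea who is admitted briefly for investigation: serious, possibly related. Some months later the same patient reports moderate dyspnoea that is neither serious nor judged related. Only the second report is kept, and the patient is tabulated as non-serious and unrelated.

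Safety and tolerability are a stated objective (protocol 2.1.3). The plan has no pre-specified safety outcome measures (protocol 7.1), no independent data monitoring committee (protocol 12.3) and no formal testing of safety data (SAP 7.6). The descriptive tables therefore carry much of the safety message, and their patient counts should be right.

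**Working it through.** The plan states no figure on this point, so there is none to reproduce. The check asks what the rule does to the possible combinations of reports.

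**Inputs.** Two reports of the same event in one patient. Each has a severity of 1 to 3 (protocol 10.4.4), is serious or not (10.1), and is related or not (10.4.2). The rule keeps the report with the higher severity (SAP 7.6, reading grade as severity).

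**Number of patterns.** Each report has 3 × 2 × 2 = 12 possible states, so two ordered reports give 12 × 12 = 144 patterns.

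**Patterns with at least one serious report.** Each report has 6 non-serious states, so 144 − 6 × 6 = 108.

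**Serious flag lost.** The milder report is serious and the more severe one is not. There are 3 ways to pick two different severities, 2 × 2 = 4 combinations of the related flags, and 2 orders: 3 × 4 × 2 = 24.

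**Undetermined.** The reports tie on severity but differ on seriousness: 3 severities × 2 (which one is serious) × 4 = 24. The SAP gives no tie-break.

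**Serious flag kept.** 108 − 24 − 24 = 60.

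**Related flag.** The same count with the roles of the two flags exchanged gives 24 lost and 24 undetermined. The trigger differs: here the milder report must be the related one, whatever its seriousness.

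**Direction.** The retained report is always one of the patient's own reports. If it is serious, the patient had a serious report; the reverse need not hold. So the number of patients counted as serious for an event cannot exceed the true number, and it can fall below it. The same holds for related.

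**Under the fix.** If each table uses its own criterion (any serious report, most related report, highest severity), 0 of the 144 patterns lose a serious or related flag, and ties no longer matter.

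**Frequency.** The 144 patterns are logical possibilities, not equally likely outcomes, so 24 of 144 is not a rate. The expected number of patients lost from the seriousness table in an arm is R × s × d. R is the number of patients with a repeated event, s the share of them with a serious report of it, and d the share of those whose retained report is not serious. The documents give none of the three. Purely as an assumed illustration, R = 20 with s and d each between 10% and 30% gives 20 × 0.10 × 0.10 = 0.2 to 20 × 0.30 × 0.30 = 1.8 patients.

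**The case against.** The strongest reply is that the rule sits between the sentence on MedDRA terms and the count-once rule for System Organ Class, so it may be meant only for those patient-level counts. That is a fair reading of its position, but the text sets no such limit. Even on that reading, the SAP does not say how a patient with discordant reports is to be classified by seriousness or causality. Grade is also undefined. Reading it as severity is an inference, though no other scale in the documents ranks general adverse events; the PLATO classes apply only to bleeding.

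It can also be said that the case is narrow. Under protocol 10.4.4 a mild event does not disturb daily life, so a mild event that is also serious will be uncommon, and the same event must then recur at a higher grade without being serious. This stands as a limit on size. It does not make the case impossible: the protocol gives its own example of a serious event that need not be severe, and under 10.1 an admission planned after randomisation counts as serious. For expectedness the effect is probably smaller still, since two reports of one event will usually be judged alike against the product information.

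Third, little is hidden overall. The listing shows each event, all bleeds are summarised by PLATO class with time to each event, and serious events go to the sponsor's office within 24 hours (protocol 10.5) and to the steering committee (12.2). This is right, and a reader who inferred that serious events vanish from the trial, or that bleeding goes unreported, would be mistaken. But PLATO classes do not show regulatory seriousness or causality, dyspnoea and bradyarrhythmia have no separate summary, and a listing does not correct a table.

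A reader might also infer that the rule flatters ticagrelor, because protocol 12.6.2 names bleeding and dyspnoea as its risks. The documents do not support that. More repeated events in one arm would not establish more discordant serious or related repeats there, and no rates are given.

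**Conclusion.** The rule is wrong as written for the seriousness and causality summaries and harmless for the severity summary. It can remove a patient from the serious count when the milder report was the serious one, and from the related count when the milder report was the related one. It can never add a patient to either.

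The size is unknown, may be small and could be zero. Any difference between the arms is equally unknown, so this is a possible undercount and not a demonstrated bias in the comparison. The conclusion assumes that grade means severity and that the rule applies to all the summaries named in SAP 7.6, as its wording allows. It should be corrected because a stated rule can produce a wrong count and the correction is simple.

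**What to change.** Amend SAP 7.6 as follows:

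- Define grade as the severity category of protocol 10.4.4, and state what counts as the same event, including when MedDRA terms are not available.
- Limit the highest-grade rule to the severity table.
- In the seriousness table, count a patient as serious for an event if any report of that event was serious.
- In the causality table use the most related report. In the expectedness table count the patient as unexpected if any report was.
- Give the number of events beside the number of patients.
- Confirm that the listing shows every report, with no de-duplication.

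The cost is a few sentences in the SAP and slightly more tabulation. The protocol already has severity and causality assessed for each adverse event, and seriousness and expectedness assessed as well, so no new data are needed.
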